1. LIST OF ABBREVIATIONS

AEs	Adverse Events
AESIs	Adverse Events of Special Interest
ALT	Alanine Transaminase (SGPT)
AST	Aspartate Transaminase (SGOT)
bid	Bis in die (twice daily)
BMI	Body Mass Index
BORR	Best Overall Response Rate
BRAF	B-raf murine sarcoma vioral oncogene homolog B1
BUN	Blood Urea Nitrogen
CI	Confidence Interval
CRP	C-reactive Protein
CT	Computed Tomography
DoR	Duration of Response
ECG	Electrocardiogram
EchO	Echocardiogram
ECOG	Eastern Cooperative Oncology Group
eCRF	Electronic Case Report Form
ENR	Enrolled Analysis Set
EORTC QLQ-C30	30-item European Organisation for Research and Treatment of Care quality of life questionnaire
EQ-5D	European Quality of Life 5-Dimensions
HGF	Hepatocyte Growth Factor
HRQoL	Health-related Quality of life
ICF	Informed Consent Form
IMP	Investigational Medicinal Product
INR	International Normalized Ratio
ITT	Intent-To-Treat Analysis Set
Kg	Kilogram
LDH	Lactate dehydrogenase
LVEF	Left Ventricle Ejection Fraction
MedDRA	Medical Dictionary for Regulatory Activities
MDSCs	Myeloid-derived Suppressor Cells
MEK	Methyl Ethyl Ketone
mg	Milligram
ml	Millilitre
MRI	Magnetic Resonance Imaging
MUGA	Multiple Gated Acquisition Scan

od	Once Daily
ORR	Overall Response Rate
OS	Overall Survival
PD	Progression of Disease
PFS	Progression-Free Survival
p.o.	Per os (oral route)
PP	Per Protocol Analysis Set
PS	Performance Status
RECIST	Response Evaluation Criteria In Solid Tumors
SAE	Serious Adverse Events
SAF	Safety Analysis Set
SAP	Statistical Analysis Plan
sCD25	Soluble interleukin-2 receptor
SECOMBIT	Sequential Combo Immuno and target Therapy
SNP	Single nucleotide polymorphism
sHGF	Soluble Hepatocyte Growth Factor
sVEGF	Serum Vascular Growth factor
T3	Triiodothyroxine
T4	Tyroxine
TPFS	Total Progression-Free Survival
TSH	Thyroid Stimulating Hormone
VAS	Visual Analog Scale
VEGF	Vascular Endothelial Growth Factor
WBC	White blood cell
WPAI:GH	Work Productivity and Activity Impairment: General Health
DMC	Data Monitoring Committee
FPFV	First Patient First Visit
LPLV	Last Patient Last Visit
C	Celsius
cm	centimetre
m	metre
SOC	System Organ Class
WHO-DRL	WHO-drug reference list
ATC	Anatomical Therapeutic Chemical
SAS	Statistical Analysis System
SDF	Survival Distribution Function
PFSR	Progression Free Survival Rate
SD	Standard Deviation

SE	Standard Error
RS	Raw Score
PT	Preferred Term
LLN	Lower Limit Of Normal
ULN	Upper Limit Of Normal
SI	International System of Units
CS	Clinically Significant
NCS	Not Clinically Significant
Min	The lowest observation
Max	The highest observation
HIV	Human Immunodeficiency Virus
[name]
mmHg	Millimeters of mercury
SBP	Systolic Blood Pressure
DBP	Diastolic Blood Pressure
bpm	beats per minute
ETDRS	Early Treatment Diabetic Retinopathy Study
OS	Left Eye
OD	Right Eye

2. INTRODUCTION

This document describes the statistical methods to be used during the analyses and reporting of study SECOMBIT. This SAP includes all details for the analysis and reporting (tables, listings and graph of the data collected as part of this protocol.

This Statistical Analysis Plan is based on the study protocol version Final 10.0, dated 03 May 2021.

3. STUDY OBJECTIVES

3.1. PRIMARY OBJECTIVE

The primary objective of this study is to define the best sequencing combination treatment in primary efficacy variable (Overall Survival, OS).

3.2. SECONDARY OBJECTIVES

The secondary objectives are to evaluate the effects of the three sequencing combination treatments on:

- Total Progression-Free Survival (PFS);
- 3 years PFS rate;
- Percentage of patients alive at 3 years;
- Best overall response rate (BORR);
- Duration of response (DoR);
- Toxicity of the investigational medicinal products (IMPs);
- Quality of life and general health status defined by:
 - Health-related quality of life (HRQoL), by means of the 30-item European Organisation for Research and Treatment of Cancer quality of life questionnaire (EORTC QLQ-C30);
 - General health status, by means of the European Quality of Life 5-Dimensions (EQ-5D) questionnaire;
 - Impairment of work productivity and activity, by means of the Work Productivity and Activity Impairment: General Health (WPAI:GH) questionnaire.

3.2.1. BIOLOGICAL MARKERS (BIOMARKERS STUDY)

The objective of the biomarker study is to focus on understanding mechanisms of action/resistance. In particular, the biomarker study:

- Will inform how to sequence targeted RAF/MEK agents with immunotherapy agents (i.e., ipilimumab and nivolumab) in melanoma;
- Will be hypothesis-generating only.

3.3. SAFETY OBJECTIVES

The safety of the sequencing combination treatments will be evaluated, in terms of:

- Toxicity of the IMPs;
- Adverse events (AEs) and serious adverse events (SAEs);
- Vital signs;
- Laboratory safety parameters.

4. STUDY DESIGN

4.1. DESCRIPTION OF THE STUDY

This is an open-label, prospective, randomized, Phase II design study.

4.2. SAMPLE SIZE

This study was designed as a phase II, randomized trial with no formal comparative test. The sample size was discussed for the primary endpoint Overall Survival (OS).

For each arm a single-stage design as described by A'Hern (A'Hern, 2001) was used.

A median PFS of about 10 months for the combo target therapy (LGX818/MEK162) was assumed (Mc Arthur et al, 2013) and a similar value for the combo immunotherapy (ipilimumab/nivolumab) derived from the aggregate clinical activity rate of 65% (Wolchock et al, 2013) which, using an exponential distribution for PFS, could broadly give a median PFS of about 9.5 months. OS seems to be strictly correlated with total PFS.

The null hypothesis was a median OS time of 15 months (i.e. percentage of surviving patient of 33% at 24 months). The alternative hypothesis was a median OS time of 23 months (i.e. percentage of surviving of 48% at 24 months).

Using an exact 5% one-sided significance test, at least 69 patients would have to be randomized in each treatment arm when the power of the study is 80%.

For each arm the strategy would be further investigated if at least 30 patients, alive at 24 months, were observed.

Taking into account a 10% drop-out rate, a total of 230 patients would be enrolled to ensure a minimum of 207 randomized patients.

4.3. DESCRIPTION OF TREATMENTS

The following IMPs will be used in the study:

- Arm A: Combo Target (LGX818 450 mg p.o. od + MEK162 45 mg p.o. bid) until PD; then Combo Immuno (nivolumab 1 mg/kg solution i.v.combined with ipilimumab 3 mg/kg solution i.v.every 3 weeks for 4 doses then nivolumab 3 mg/kg solution i.v.every 2 weeks) until PD.
- Arm B: Combo Immuno (nivolumab 1 mg/kg solution i.v.combined with ipilimumab 3 mg/kg solution i.v.every 3 weeks for 4 doses then nivolumab 3 mg/kg solution i.v.every 2 weeks) until PD; then Combo Target (LGX818 450 mg p.o. od + MEK162 45 mg p.o. bid) until PD.
- Arm C: Combo Target (LGX818 450 mg p.o. od + MEK162 45 mg p.o. bid) for 8 weeks followed by Combo Immuno (nivolumab 1 mg/kg solution i.v.combined with ipilimumab 3 mg/kg solution i.v.every 3 weeks for 4 doses then nivolumab 3 mg/kg solution i.v.every 2 weeks) until PD; then Combo Target (LGX818 450 mg p.o. od + MEK162 45 mg p.o. bid) until PD.

4.4. DESCRIPTION OF THE STUDY FLOW

The study will be conducted according to an open-label, prospective, randomized, phase II design.

Randomization will be stratified according to stage arranged in the 3 following strata:

- IIIb/c – M1a – M1b;
- M1c with normal LDH (≤ 2 ULN);

- M1c with elevated LDH (> 2 ULN).

All screening/baseline assessments as outlined in Tables 1 of the protocol (arm A), 2 (arm B) and 3 (arm C) of the Study Protocol must be performed within 28 days prior to the first administration of study drugs on Day 1. Results of tests or examinations performed as standard of care before obtaining informed consent and within the 28 days prior to commencing study drugs may be used. All assessments during the study must be performed within a window +/-3 days of the day indicated on the schedule of assessment, except for tumor evaluations for which a window of +/- 7 days will apply and for Combo Immuno visits for which a window of +/- 2 days will apply.

Eligibility for the study will be determined by the Investigator from the mandatory screening/baseline assessments performed during screening and according to the study inclusion/exclusion criteria.

First dosing of study drugs will be determined by the patient's eligibility and the laboratory assessments done on Day 1 prior to dosing.

Hematology and biochemistry assessments do not need to be repeated on Day 1 if performed within 7 days; if it is necessary to repeat these blood tests, the results must be known before the patient receives treatments to ensure inclusion/exclusion criteria related to these tests are met. Test for HIV infection is mandatory at screening.

Subject Re-enrollment: This study permits the re-enrollment of patients that was not randomized within 28 from ICF signature, after obtaining agreement from the medical monitor prior to re-enrolling a subject. If authorized to re-enrollment, the patient must be re-consented and the same subject-code can be used.

Subjects will be assessed for response by computed tomography (CT) or Magnetic Resonance Imaging (MRI). All measurable and non-measurable lesions must be documented at screening (within 28 days prior to randomization) and re-assessed at each subsequent tumor evaluation (every 8 weeks (+/- 1 week) for the first year, every 12 weeks (+/- 1 week) while the patient is on study). Tumor assessments with CT or MRI scans of the brain, chest, abdomen, and pelvis will be performed until disease progression after the second combo treatment per RECIST v1.1.

For patients who discontinue study treatment for reason other than investigator-determined disease progression, tumor assessments should continue to be performed as scheduled.

Patients will continue to be on study and can be switched to the subsequent therapy after PD as per protocol in both arm A and B.

In case of an interruption of the treatment in arm C, reason other than investigator-determined disease progression, during the first 8 weeks (2 cycles of therapy), patient can continue the study treatment with combo immuno, as scheduled.

For patients with palpable/superficial lesions, clinical disease assessments by physical examination should be performed at baseline and throughout study treatment as clinically indicated. Color photographs with ruler/calipers will be taken at baseline and at all subsequent tumor assessment time points.

The National Cancer Institute Common Toxicity Criteria for Adverse Events (NCI CTC-AE) Version 4.03 will be used to evaluate the clinical safety of the treatment in this study. Patients will be assessed for AEs at each clinical visit and as necessary throughout the study.

Biomarker study

A correlative biological study will be performed for the evaluation of biomarkers on the biological sample available (paraffin-embedded tissue, frozen tissue, blood, serum, etc.). Approximately 80-90 patients will take part in the biomarker study.

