21.1. ADVERSE EVENTS

All adverse events (AEs) reported on eCRF and experienced by the patient on or after the informed consent date will be considered in the analysis. Thus, there will not be derivation to Treatment-emerged Adverse Events (TEAE) and not TEAE.

Adverse event Investigator terms will be assigned to a Preferred Term (PT) and will be classified by primary System Organ Class (SOC) according to the Medical Dictionary for Regulatory Activities (MedDRA) thesaurus, version 20.0 or higher

Counts and percentages will be presented by primary System Organ Class (SOC) and Preferred Term (PT) as defined in MedDRA thesaurus, by treatment arm.

A patient having more than one AE with the same PT will be counted only once in the incidence calculation for that PT. Similarly, if a patient has more than one AE in the same SOC, the patient will be counted only once in the total number of patients with an AE for that SOC.

An AE will be defined “Related” if causality is “Certain”, “Probable” or “Possible”.

The following frequency distributions of adverse events will be provided by treatment arm:

- An overview of AEs including the number of patients with:
 - at least one AE,
 - at least one non-serious AE,
 - at least one AE related to Ipilimumab,
 - at least one AE related to Nivolumab,
 - at least one AE related to Combo Immuno Therapy,
 - at least one AE related to LGX818,
 - at least one AE related to MEK162,
 - at least one AE related to Combo Target Therapy,
 - at least one serious AE (SAE),
 - at least one SAE related to Ipilimumab,
 - at least one SAE related to Nivolumab,
 - at least one SAE related to Combo Immuno Therapy,
 - at least one SAE related to LGX818,
 - at least one SAE related to MEK162,
 - at least one SAE related to Combo Target Therapy,
 - at least one AE leading to hospitalization,
 - at least one AE leading to withdrawal from the study,

- at least on AESI,
and the number of AEs, non-serious AEs, SAEs, AEs related to Ipilimumab, AEs related to Nivolumab, AEs related to Combo Immuno Therapy, AEs related to LGX818, AEs related to MEK162, AEs related to Combo Target Therapy, SAEs related to Ipilimumab, SAEs related to Nivolumab, SAEs related to Combo Immuno Therapy, SAEs related to LGX818, SAEs related to MEK162, SAEs related to Combo Target Therapy, AEs leading to hospitalization, AEs leading to death, AEs leading to study withdrawal, AESIs;
- AEs presented by Primary SOC and PT;

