- AEs related to Ipilimumab presented by Primary SOC and PT;
- AEs related to Nivolumab presented by Primary SOC and PT;
- AEs related to Combo Immuno Therapy presented by Primary SOC and PT;
- AEs related to LGX818 presented by Primary SOC and PT;
- AEs related to MEK162 presented by Primary SOC and PT;
- AEs related to Combo Target Therapy presented by Primary SOC and PT;
- Serious AEs presented by Primary SOC and PT;
- AEs leading to hospitalization presented by Primary SOC and PT;
- AEs leading to death presented by Primary SOC and PT;
- AEs leading to study withdrawal presented by Primary SOC and PT.
- AESIs presented by Primary SOC and PT

The following individual data listings will be produced:

- A listing of all AEs;
- A listing of AEs related to Ipilimumab;
- A listing of AEs related to Nivolumab;
- A listing of AEs related to Combo Immuno Therapy;
- A listing of AEs related to LGX818;
- A listing of AEs related to MEK162;
- A listing of AEs related to Combo Target Therapy;
- A listing of all SAEs;
- A listing of all AEs leading to death;
- A listing of AEs leading to hospitalization;
- A listing of AEs leading to study withdrawal;
- A listing of AESIs.

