Source: XXXX.SAS, Run on DDMMYYYY

TABLE 46. Incidence of AEs by primary System Organ Class and Preferred Term

POPULATION: SAF

	Statistic	Arm A (N = XX)	Arm B (N = XX)	Arm C (N = XX)
<Primary SOC>	n (%) E	xx (xx.x%) xx	xx (xx.x%) xx	xx (xx.x%) xx
<PT>	n (%) E	xx (xx.x%) xx	xx (xx.x%) xx	xx (xx.x%) xx
<PT>	n (%) E	xx (xx.x%) xx	xx (xx.x%) xx	xx (xx.x%) xx
<PT>	n (%) E	xx (xx.x%) xx	xx (xx.x%) xx	xx (xx.x%) xx
<Primary SOC>	n (%) E	xx (xx.x%) xx	xx (xx.x%) xx	xx (xx.x%) xx
<PT>	n (%) E	xx (xx.x%) xx	xx (xx.x%) xx	xx (xx.x%) xx
<PT>	n (%) E	xx (xx.x%) xx	xx (xx.x%) xx	xx (xx.x%) xx
<PT>	n (%) E	xx (xx.x%) xx	xx (xx.x%) xx	xx (xx.x%) xx
<Primary SOC>	n (%) E	xx (xx.x%) xx	xx (xx.x%) xx	xx (xx.x%) xx
<PT>	n (%) E	xx (xx.x%) xx	xx (xx.x%) xx	xx (xx.x%) xx
<PT>	n (%) E	xx (xx.x%) xx	xx (xx.x%) xx	xx (xx.x%) xx
<PT>	n (%) E	xx (xx.x%) xx	xx (xx.x%) xx	xx (xx.x%) xx
<Primary SOC>	n (%) E	xx (xx.x%) xx	xx (xx.x%) xx	xx (xx.x%) xx
<PT>	n (%) E	xx (xx.x%) xx	xx (xx.x%) xx	xx (xx.x%) xx
<PT>	n (%) E	xx (xx.x%) xx	xx (xx.x%) xx	xx (xx.x%) xx
<PT>	n (%) E	xx (xx.x%) xx	xx (xx.x%) xx	xx (xx.x%) xx

Note: a) Percentages are calculated relative to the total number of patients in the SAF Population by treatment arm.

b) Each patient is counted at most once within each SOC and PT.

c) AEs were coded using MedDRA version 20.0.

d) n = number of patients, E = number of events.

Source: XXXX.SAS, Run on DDMMYYYY

TABLE 47. Incidence of Ipilimumab-related AEs by primary System Organ Class and Preferred Term

POPULATION: SAF

	Statistic	Arm A (N = XX)	Arm B (N = XX)	Arm C (N = XX)
<Primary SOC>	n (%) E	xx (xx.x%) xx	xx (xx.x%) xx	xx (xx.x%) xx
<PT>	n (%) E	xx (xx.x%) xx	xx (xx.x%) xx	xx (xx.x%) xx
<PT>	n (%) E	xx (xx.x%) xx	xx (xx.x%) xx	xx (xx.x%) xx
<PT>	n (%) E	xx (xx.x%) xx	xx (xx.x%) xx	xx (xx.x%) xx
<Primary SOC>	n (%) E	xx (xx.x%) xx	xx (xx.x%) xx	xx (xx.x%) xx
<PT>	n (%) E	xx (xx.x%) xx	xx (xx.x%) xx	xx (xx.x%) xx
<PT>	n (%) E	xx (xx.x%) xx	xx (xx.x%) xx	xx (xx.x%) xx
<PT>	n (%) E	xx (xx.x%) xx	xx (xx.x%) xx	xx (xx.x%) xx
<Primary SOC>	n (%) E	xx (xx.x%) xx	xx (xx.x%) xx	xx (xx.x%) xx
<PT>	n (%) E	xx (xx.x%) xx	xx (xx.x%) xx	xx (xx.x%) xx
<PT>	n (%) E	xx (xx.x%) xx	xx (xx.x%) xx	xx (xx.x%) xx
<PT>	n (%) E	xx (xx.x%) xx	xx (xx.x%) xx	xx (xx.x%) xx
<Primary SOC>	n (%) E	xx (xx.x%) xx	xx (xx.x%) xx	xx (xx.x%) xx
<PT>	n (%) E	xx (xx.x%) xx	xx (xx.x%) xx	xx (xx.x%) xx
<PT>	n (%) E	xx (xx.x%) xx	xx (xx.x%) xx	xx (xx.x%) xx

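### CTC-AE grade is named for evaluating safety and is collected, but no AE summary uses it, so toxicity is only partly described by sequence

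*Supplement*

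**What the plan says.** Table numbers here are those printed on the shells. The list at the start of Section 26 numbers the same AE tables two lower (43 to 55).

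- **Scale.** Section 4.4 names NCI CTC-AE version 4.03 as the criteria that "will be used to evaluate the clinical safety of the treatment in this study".
- **Objective.** Section 3.2 makes toxicity of the study drugs a secondary objective, and Section 3.3 repeats it as a safety objective: "Toxicity of the IMPs".
- **Basis of the summaries.** Section 21.1: "Counts and percentages will be presented by primary System Organ Class (SOC) and Preferred Term (PT) as defined in MedDRA thesaurus, by treatment arm". The outputs it lists are all AEs, AEs related to each drug and each combination, serious AEs ("Serious AEs presented by Primary SOC and PT"), fatal AEs ("AEs leading to death presented by Primary SOC and PT"), AEs leading to hospitalization or to withdrawal, and AESIs. The overview also has non-serious AEs and related serious AEs.
- **Counting rule.** The SOC/PT shells state only this: "Each patient is counted at most once within each SOC and PT".
- **Grade.** It appears as a column in AE Listings 54 to 65 and in no AE table.
- **Scope.** Section 2 says "This SAP includes all details for the analysis and reporting", and Section 10 says that the templates set the format and content of what will be delivered.

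**The concern.** The plan names a severity scale for safety and collects the grade, but the summaries by arm stop short of using it. A programmer who follows Section 21.1 and the shells will produce no figure by arm for grade 3 or higher events. Because Section 8.3 rules out comparative tests, the descriptive tables are the safety result; what they leave out is not reported elsewhere by arm.

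Two features of this trial make rows that mix all grades less informative than usual. All three sequences plan both combinations (Section 4.3), so patients in every arm may receive the same four drugs. And Section 21.1 counts every AE from informed consent, with no treatment-emergent derivation. Both push the row for patients with at least one AE towards similar values in the three arms, while the sequences may differ in how severe the events are.

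**Working it through.** The plan states no figure on this point, so there is none to reproduce. The check sets the outputs side by side and asks where an event of a given grade would be counted.

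| Event | Where the summaries count it, beyond the all-AE and related-AE rows |
|---|---|
| Serious, any grade | SAE and related-SAE rows of Table 45; Table 53 |
| Leads to hospitalization | Hospitalization rows of Table 45; Table 54 |
| Leads to withdrawal | Withdrawal rows of Table 45; Table 55 |
| AESI | AESI rows of Table 45; Table 56 |
| Fatal | Event count in Table 45; Table 57 |
| Grade 3 or 4, non-serious, none of these flags | Only the non-serious rows of Table 45 |
| Grade 1, non-serious, none of these flags | Only the non-serious rows of Table 45 |

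The last two lines are identical. Both events also enter Table 46, and Tables 47 to 52 if related, in the same cells. Nothing in any AE table separates them.

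Two other places might have filled the gap, and neither does:

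1. Listings 54 to 65 show grade per patient and event. They give no incidence, and their shells have no treatment-arm column.
2. Section 21.2 summarises laboratory results as values and changes from baseline, with no CTC-AE grading and no shift table. A non-serious grade 3 or 4 laboratory abnormality is therefore not picked up there by grade.

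**Illustration only.** The documents give no AE rates, so every rate below is assumed. The 69 patients per arm come from Section 4.2. The interval is the Wilson 95% interval, with p = x/n and z = 1.96:

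[p + z²/(2n) ± z·√(p(1−p)/n + z²/(4n²))] / (1 + z²/n)

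| Assumed rate | Patients of 69 | 95% interval |
|---|---|---|
| Any grade, 90% | 62 | 80.5% to 95.0% |
| Any grade, 95% | 66 | 88.0% to 98.5% |
| Any grade, 99% | 68 | 92.2% to 99.7% |
| Grade 3 or higher, 30% | 21 | 20.8% to 42.1% |
| Grade 3 or higher, 40% | 28 | 29.8% to 52.4% |
| Grade 3 or higher, 50% | 34 | 37.8% to 60.8% |
| Grade 3 or higher, 60% | 41 | 47.6% to 70.2% |

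Two arms could both show 66 of 69 patients with at least one AE while one had 21 and the other 41 patients with a grade 3 or higher event. That is a difference of 20/69 = 29.0 percentage points. The SAE, hospitalization, withdrawal and AESI rows might reflect part of that difference. How much depends on the share of those events that carry such a flag, which the documents do not give.

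**The case against.** The strongest case on the other side has three parts.

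*Section 4.4 makes no promise of a table by grade.* It names the criteria in the description of study flow, next to a sentence about assessing AEs at visits, and can be read as a rule for recording. This stands. A reader might infer that the plan contradicts itself; the text does not go that far, and the Grade column in the listings satisfies the narrow reading. What remains is that a scale named for evaluating safety feeds no summary by arm.

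*The plan has other severity information.* This stands too. A reader might infer that the toxicity objective rests on any-grade incidence alone, or that the planned tables cannot separate the sequences. Neither is supported. Table 45 gives serious AEs, serious AEs related to each drug and combination, hospitalizations, withdrawals and AESIs, and Tables 53 to 57 break down serious, hospitalization, withdrawal, AESI and fatal events by SOC and PT. Nothing in the documents puts those rates near a ceiling. But these categories are defined by seriousness, consequence or topic rather than by grade, so they cover severity only in part. AESI is not defined in the text available, so how much it captures is unknown.

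*Nothing decisive changes.* Correct. The rule for taking an arm further is at least 30 patients alive at 24 months (Section 4.2), the results are descriptive, and grade is collected, so a table could be made later. That limits the weight of the point. It does not remove the value of fixing the output and the counting rule before the data are summarised.

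The protocol was not available for this check. Table content is an SAP matter, however, and Sections 2 and 10 present this SAP and its templates as complete.

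**Conclusion.** The gap is real and limited. No AE summary in Section 21.1 or Tables 45 to 57 uses CTC-AE grade, although the scale is named for evaluating safety and the grade is collected. The outputs based on seriousness and consequence describe severity in part. Non-serious grade 3 or 4 events without another flag appear only in rows that mix all grades, so the toxicity objective is incompletely described by sequence.

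The size cannot be computed from the documents; the 29-point illustration rests wholly on assumed rates. No stated figure, test or decision rule changes. This is an inexpensive reporting improvement worth making, not an error in the design or in the efficacy analysis.

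**What to change.** 1. In Section 21.1 and Table 45, add the number and percentage of patients with at least one grade 3 or higher AE, and with at least one grade 3 or higher related AE, for each of the four drugs and both combinations.
2. Present Tables 46 to 52 by worst grade per patient, in two columns within each arm: any grade, and grade 3 or higher.
3. State the counting rule: within each SOC and each PT, a patient is counted once, at the highest grade recorded. Say how a missing grade is shown; a separate line would fit Section 9.3, which rules out imputation.

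A grade 5 split of Table 46 is not needed, because Table 57 already covers fatal AEs.

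The cost is extra programming and more tables to review. No new data are needed, since grade is already in the AE listings.
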